8.2.3.2 Safety Endpoints

Safety measurements are described in Section 4.2.3.2 Safety Endpoints and Section 7.

Safety and tolerability will be assessed by clinical review of all relevant parameters including adverse events (AEs), laboratory tests, and vital signs. Safety parameters to be analyzed include, but are not limited to, AEs, SAEs, fatal AEs, and laboratory changes. Furthermore, specific events will be collected and designated as events of clinical interest (ECIs) as described in Section 7.2.3.2.

8.2.3.3 Biomarker Endpoints

A separate biomarker SAP will be provided for the following endpoints/analyses.

- The association between PD-L1 protein expression by IHC and antitumor activity to pembrolizumab as monotherapy for mTNBC.
- The association between antitumor activity of pembrolizumab in mTNBC and efficacy/resistance biomarkers, utilizing tumor and blood specimens obtained before/after treatment and at disease progression.
- The performance comparison of PD-L1 assessment by IHC in newly-obtained vs. archived tumor samples.

8.2.3.4 Pharmacokinetic Endpoints

Pharmacokinetic parameters and the presence of anti-drug antibodies, following IV administration of 200 mg pembrolizumab Q3W as monotherapy in subjects with mTNBC (details see Section 4.2.3.4.)

8.2.3.5 Other Endpoints

Other endpoints include association between genetic variation and response to the treatment(s) administered, variation across the human genome for the association with clinical data (details see Sections 4.2.3.5 and 4.2.3.6.) and the association between LDH and efficacy response to pembrolizumab as monotherapy for mTNBC.

8.2.4 Analysis Populations

8.2.4.1 Efficacy Analysis Populations

The All-Subjects-as-Treated (ASaT) population, which consists of all enrolled subjects who receive at least one dose of study medication with measurable metastatic disease at baseline, will serve as the primary population for the analyses of efficacy data in this trial.

Details on the approach to handling missing data for efficacy analyses are provided in Section 8.2.5 Statistical Methods.

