3.0 OBJECTIVE(S) & HYPOTHESIS(ES)

3.1 Primary Objective(s) & Hypothesis(es)

1. **Objective (Cohort A):** To estimate the Objective Response Rate (ORR) to pembrolizumab as 2L+ monotherapy for PD-L1 (+) centrally confirmed mTNBC and centrally confirmed mTNBC independent of PD-L1 status (all comers), based on RECIST 1.1 as assessed by the central imaging vendor.
2. **Objective (Cohorts A+C):** To estimate the ORR to pembrolizumab as 2L+ monotherapy in subjects with PD-L1 strong (+) centrally confirmed mTNBC, based on RECIST 1.1 as assessed by the central imaging vendor.
3. **Objective (Cohorts A-C):** To determine the safety and tolerability of pembrolizumab monotherapy for mTNBC across cohorts and by PD-L1 status within lines of treatment for mTNBC.

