 - b. Note: If emerging data demonstrates that there is no difference in the clinical utility of PD-L1 assessment in newly obtained samples relative to archived ones, then archived samples may be acceptable without Sponsor agreement. If this is the case, sites will be notified via an Administrative Memo.
 - c. Note: For subjects with mTNBC at the time of initial breast cancer diagnosis, who did not have breast surgery and/or breast radiation therapy, a newly obtained core or excisional biopsy from the existing breast tumor mass may be obtained for eligibility determination.
9. Have measurable metastatic disease based on RECIST 1.1 as determined by the central imaging vendor. Tumor lesions situated in a previously irradiated area are considered measurable, if radiographic progression has been demonstrated in such lesions.
 - a. Note: The same imaging modality, acquisition and technical parameters should be used throughout the study for tumor imaging.
10. Have a performance status of 0 or 1 on the ECOG Performance Scale. Assessment should be performed within 10 days of treatment initiation.
11. Female subjects of childbearing potential should be willing to use 2 methods of birth control or be surgically sterile, or abstain from heterosexual activity for the course of the study through 120 days after the last dose of study medication (Reference Section 5.7.2). Subjects of childbearing potential are those who have not been surgically sterilized or have not been free from menses for > 1 year.

Male subjects should agree to use an adequate method of contraception starting with the first dose of study therapy through 120 days after the last dose of study therapy.

Abstinence is acceptable if this is the usual lifestyle and preferred contraception for the subject.
12. Demonstrate adequate organ function as defined in [Table 2](#). All screening labs should be performed within 10 days of treatment initiation.

Table 2 Adequate Organ Function Laboratory Values

System	Laboratory Value
Hematological	
Absolute neutrophil count (ANC)	≥1,500 /mCL
Platelets	≥100,000 / mCL
Hemoglobin	≥9 g/dL or ≥5.6 mmol/L without transfusion or EPO dependency
Renal	
Creatinine OR Measured or calculated ^a creatinine clearance (CrCl)	≤1.5 X upper limit of normal (ULN) OR ≥30 mL/min for subject with creatinine levels > 1.5 X institutional ULN
[Glomerular filtration rate (GFR) can also be used in place of creatinine or CrCl]	
Hepatic	

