7.1.2.6.1 Baseline Tumor Imaging

To meet screening criteria, tumor imaging must be performed within 28 days prior to the date of allocation. The baseline tumor imaging (CT strongly preferred) should be submitted immediately to the central imaging vendor for determination of measurable disease per RECIST 1.1 and inclusion into the study. Central imaging vendor confirmation of this eligibility criterion is required prior to allocation of the subject.

Tumor imaging performed as part of routine clinical management are acceptable for use as the screening imaging if they are of diagnostic quality, meet the requirements specified in the SIM, and are performed within 28 days prior to the date of allocation.

In addition, brain imaging is required at screening for all subjects to confirm that there are no detectable brain metastases present at baseline. MRI is the preferred imaging modality however CT is acceptable if an MRI is clinically contraindicated.

A bone scan should be performed at screening for all subjects with known bone metastases or active bone pain, and for subjects with new symptoms concerning of osseous metastasis [e.g., new bone pain and/or new persistently elevated alkaline phosphatase (AP)].

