7.1.2.6.4 RECIST 1.1

RECIST 1.1 will be applied by the central imaging vendor retrospectively as the primary measure for assessment of tumor response. All tumor imaging should be submitted to the central imaging vendor.

7.1.2.6.5 irRECIST

irRECIST is RECIST 1.1 adapted as described below to account for the unique tumor response seen with immuno-therapeutics.

irRECIST will be used by site investigators and local radiology review to assess tumor response and progression, and make treatment decisions. This data will be collected in the clinical database.

irRECIST will be used by the central imaging vendor, however, this evaluation will be done retrospectively.

irRECIST takes into account the clinical condition/stability of subjects, as described in [Table 6](#), in addition to response or progression via tumor imaging

Clinically stable is defined by the following criteria:

- Absence of symptoms and signs indicating clinically significant progression of disease, including worsening of laboratory values
- No decline in ECOG performance status
- Absence of rapid progression of disease
- Absence of progressive tumor at critical anatomical sites (e.g., cord compression) requiring urgent alternative medical intervention

Table 6 irRECIST: Tumor Imaging and Treatment after 1st Radiologic Evidence of PD or SD, CR or PR

	Clinically Stable		Clinically Unstable	
	Tumor Imaging	Treatment	Tumor Imaging	Treatment
1 st radiologic evidence of PD	Repeat tumor imaging at ≥ 4 weeks at site to confirm PD	May continue study treatment at the site Investigator's discretion while awaiting confirmatory scan by site	Repeat tumor imaging at ≥ 4 weeks to confirm PD by the site investigator/local radiology review	Discontinue treatment
Repeat tumor imaging confirms PD	No additional tumor imaging required	Discontinue treatment (exception is possible upon consultation with Sponsor).	No additional tumor imaging required	N/A
Repeat tumor imaging shows SD, PR or CR	Continue regularly scheduled tumor imaging assessments	Continue study treatment at the site Investigator's discretion	Continue regularly scheduled tumor imaging assessments	May restart study treatment if condition has improved and/or clinically stable per site Investigator's discretion. Next tumor imaging should occur according to the every 9 week (63 \pm 7 days) imaging schedule in the first year or every 12 weeks after one year.

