8.1 Statistical Analysis Plan Summary

This section contains a brief summary of the statistical analyses for this trial. Full detail is in the Statistical Analysis Plan (SAP) (Section 8.2).

In addition, a separate analysis plan document will be issued prior to biomarker unblinding for each of the following laboratory procedures and assessments: (1) Biomarkers (detailed in Section 7.1.3.4 and 7.1.3.5) and their association with antitumor efficacy and (2) Pharmacokinetic and pharmacodynamics evaluation (detailed in Section 7.1.3.3)

Study Design Overview	A Phase II Clinical Trial of Pembrolizumab as Monotherapy in Subjects with Metastatic Triple-Negative Breast Cancer (mTNBC)
Treatment Assignment	Treatment assignment is open label.
Analysis Populations	Efficacy: All Subjects as Treated (ASaT) Safety: All Subjects as Treated (ASaT)
Primary Endpoint(s)	Objective Response Rate (ORR)
Statistical Methods for Key	ORR estimation

Efficacy Analyses	
 • 2L+ population 
 ○ PD-L1 (+) population (Cohort A) ○ Overall population (Cohort A) ○ PD-L1 strong (+) population (Cohorts A+C) • 1L population (Cohort B) • Counts and percentages • 95% Agresti-Coull confidence intervals
Statistical Methods for Key Safety Analyses	Counts and percentages of AEs will be provided. Confidence intervals for rates of AEs of clinical interest will be computed using the exact binomial method.
Interim Analyses	
 • Futility analysis for 2L+ subjects (Cohort A) with PD-L1 (-) tumors based on no progression 
 ○ ~25 PD-L1 (-) subjects ○ If no response or stable disease, continue 2L+ population (Cohort A) in PD-L1 (+) patients only • Evaluation of expansion to Cohort C for PD-L1 strong (+) population based on ORR. 
 ○ ~10 patients evaluable through response, progression or 18-week scan, whichever comes first. ○ Cohort C may start if ≥ 1 responses observed 
The final analysis of Cohorts A and C combined is to be completed when subjects are evaluable through response, progression or 18-week scan, whichever comes first.

Multiplicity	This is an estimation study. No multiplicity adjustment will be applied.

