8.2.4.2 Safety Analysis Populations

The All-Subjects-as-Treated (ASaT) population will be used for the analysis of safety data. At least one laboratory or vital sign measurement obtained subsequent to at least one dose of study treatment is required for inclusion in the analysis of each specific parameter. To assess change from baseline, a baseline measurement is also required.

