8.2.11 Extent of Exposure

Extent of Exposure for a subject is defined as number of cycles in which the subject receives the study medication infusion. Summary statistics will be provided on Extent of Exposure for ASaT population.

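### The set used for safety and exposure inherits a measurable-disease condition, so a dosed subject who lacks measurable disease falls outside every safety table

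*Combined protocol and SAP*

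**What the plan says.** Protocol 8.2.4.1, under the heading for efficacy populations, states that the ASaT set "consists of all enrolled subjects who receive at least one dose of study medication with measurable metastatic disease at baseline". sSAP 3.5.1 repeats this word for word. The definition has three conditions: enrolment, a dose, and measurable disease on entry. It names no assessor for the third.

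Protocol 8.2.4.2 then says: "The All-Subjects-as-Treated (ASaT) population will be used for the analysis of safety data". sSAP 3.5.2 says the same. Both add only that laboratory and vital-sign summaries need a post-dose value, and a baseline value where change is analysed. Neither redefines the set. The summary tables in protocol 8.1 and sSAP 3.1 list the same set for efficacy and for safety ("Safety: All Subjects as Treated (ASaT)"). Protocol 8.2.11 and sSAP 3.12 use it for exposure: "Summary statistics will be provided on Extent of Exposure for ASaT population".

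The third primary objective in protocol 3.1, covering Cohorts A-C, is "To determine the safety and tolerability of pembrolizumab monotherapy for mTNBC across cohorts and by PD-L1 status within lines of treatment". It carries no imaging restriction.

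On entry, inclusion criterion 9 in protocol 5.1.2 requires subjects to "Have measurable metastatic disease based on RECIST 1.1 as determined by the central imaging vendor", and 7.1.2.6.1 adds: "Central imaging vendor confirmation of this eligibility criterion is required prior to allocation of the subject". Later in the trial, under 7.1.2.6.4, "RECIST 1.1 will be applied by the central imaging vendor retrospectively as the primary measure for assessment of tumor response".

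**The concern.** Whether a lesion can be measured is relevant to whether a response can be assessed. It has no bearing on whether a treated person had an adverse event. A condition that makes sense for the response-rate denominator has been carried into the safety set because both share one name and one definition. The name itself, all subjects as treated, suggests that no such exclusion was meant, so name and definition disagree, and a programmer who follows the definition would apply the exclusion.

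At stake is the completeness of the safety and exposure tables. An excluded subject takes their events out of the numerator and themselves out of the denominator. For common events the effect is slight. For a rare or fatal event it can decide whether the event appears at all.

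A second, smaller gap is that the definition does not say whose reading of the baseline scan decides membership, although more than one reading is made during the trial.

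**Working it through.** **1. Is there a dose-only definition anywhere?** I set the places that name the safety or exposure population side by side.

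| Place | Set named | Own definition? |
|---|---|---|
| Protocol 8.1, sSAP 3.1 (summary tables) | ASaT for efficacy and safety | No |
| Protocol 8.2.4.1, sSAP 3.5.1 | ASaT for efficacy | Yes, with the measurable-disease condition |
| Protocol 8.2.4.2, sSAP 3.5.2 | ASaT for safety | No |
| Protocol 8.2.11, sSAP 3.12 | ASaT for exposure | No |

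The only definition is the one with the imaging condition, so the literal reading stands. In addition, sSAP 3.11 summarises days on therapy for an FAS population. FAS is spelled out in the protocol's abbreviation list (12.5) but defined in neither document.

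**2. Who could be affected?** Measurable disease must be confirmed centrally before allocation. A dosed subject without it should therefore arise only if someone is treated in breach of that rule, or if a later reading of the baseline scan were allowed to overrule the first. The documents give no number for either.

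**3. The plan's own safety precision.** Tables 14 and 16 of protocol 8.2.7 give exact (Clopper-Pearson) 95% intervals. For x events in n subjects,

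- lower limit = 2.5% quantile of Beta(x, n − x + 1)
- upper limit = 97.5% quantile of Beta(x + 1, n − x)

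For x = 8, n = 80 this gives 10.0% (4.4, 18.8), as printed in Table 16. All ten rows of the two tables reproduce to the printed decimal.

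**4. Effect of the condition.** Suppose 80 subjects are dosed and 8 have the event. The number without measurable disease, m, is an assumption for illustration.

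| m | Events among them | Set as written | Rate (exact 95% CI) |
|---|---|---|---|
| 0 | 0 | 8/80 | 10.0% (4.4, 18.8) |
| 1 | 0 | 8/79 | 10.1% (4.5, 19.0) |
| 1 | 1 | 7/79 | 8.9% (3.6, 17.4) |
| 2 | 2 | 6/78 | 7.7% (2.9, 16.0) |

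Under a dose-only definition every row would read 8/80.

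**5. A single rare event.** If all 285 planned subjects are dosed and the only case occurs in an excluded subject, 1/285 (exact 95% CI 0.0 to 1.9%) becomes 0/284 (0.0 to 1.3%). The event is then absent from the table.

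**6. A comparison inside the protocol.** Section 4.2.1 reports the earlier Phase Ib TNBC cohort (KN 012) with two denominators. Drug-related serious events are five patients, 15.6%, which is 5/32, all those enrolled. Responses are one complete and four partial among the 27 with centrally confirmed measurable disease, which is 5/27 = 18.5%. Efficacy and safety were kept apart there; this plan merges them.

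**The case against.** The strongest reply is that the problem is almost empty. The central vendor must confirm measurable disease before anyone is allocated, so the condition should exclude close to nobody. Adverse events, serious events and events of clinical interest are reported to the sponsor without any imaging condition (protocol 7.2, 7.2.3.1, 7.2.3.2), so an affected subject's events would still be collected. Both points stand and keep the matter small. They do not cure it. Collection is not tabulation, and a safety set has nothing to gain from the condition.

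The gap over which reading decides is also narrower than it looks. Protocol 7.1.2.6.1, which deals with baseline imaging, sends the scans to the central vendor to determine measurability. That makes the eligibility read the natural referent of the ASaT wording, even though the definition does not say so.

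A reader might go further and infer that the retrospective central read could strip subjects from the ORR denominator after treatment and so shift the responder counts at which the lower confidence limit passes 10%. The documents do not support this. Protocol 7.1.2.6 and 7.1.2.6.4 describe the retrospective read only for response and progression, and nothing says that it reopens baseline measurability. The 10% statements in 8.2.7 are planning illustrations in a trial that 8.2.2 and 8.2.6 describe as estimation, with no success criterion attached.

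Nor should the 5 of 32 KN 012 patients outside the response denominator be taken as a forecast for this trial. The documents do not say that KN 012 required central confirmation before enrolment.

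**Conclusion.** The safety and exposure populations are wrong as written. They carry a measurable-disease condition that belongs to efficacy, and no other passage removes it. This rests on the text alone.

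The likely size is small. The number affected should be close to zero given central confirmation before allocation, and no rate can be drawn from the documents. If no such subject is dosed, nothing changes. If one is, and had the event, a rate of 8/80 (10.0%) becomes 7/79 (8.9%), and an isolated rare event can be lost altogether.

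For ORR, all that is warranted is a one-line clarification that the pre-allocation central read governs. No bias in the response rate has been shown.

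**What to change.** In protocol 8.2.4.2 and sSAP 3.5.2, define the safety set as everyone enrolled who was given any dose of pembrolizumab, with no imaging condition, and use that set for exposure in protocol 8.2.11 and sSAP 3.12.

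In protocol 8.2.4.1 and sSAP 3.5.1, give the efficacy set its own name and keep the measurable-disease condition there. Add one line: membership is decided by the central vendor's eligibility read made before allocation, and later readings do not change it. No subject can then leave the ORR denominator after treatment. The existing rule that missing response data count as non-response covers the rest, so no special response rule is needed.

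The cost is a few sentences plus consistent population names in the summary tables (protocol 8.1, sSAP 3.1) and the analysis-strategy tables (protocol Table 10, sSAP Table 2). The undefined FAS in sSAP 3.11 should be reconciled in the same pass. No planned sample size or analysis method changes.

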8.2.4.2 Safety Analysis Populations

The All-Subjects-as-Treated (ASaT) population will be used for the analysis of safety data. At least one laboratory or vital sign measurement obtained subsequent to at least one dose of study treatment is required for inclusion in the analysis of each specific parameter. To assess change from baseline, a baseline measurement is also required.

8.2.5 Statistical Methods

8.2.5.1 Statistical Methods for Efficacy Analyses

Efficacy of pembrolizumab as 2L+ monotherapy for mTNBC will be evaluated primarily in PD-L1 (+) and overall population (all comers) in Cohort A, and also in subjects with PD-L1 strong (+) tumors from Cohorts A and C combined. Cohort A will be evaluated for association between PD-L1 biomarker expression and antitumor activity. A separate biomarker SAP will be devoted to association between PD-L1 biomarker expression and antitumor activity analysis.

The primary efficacy endpoints are ORR based on RECIST 1.1 by the central imaging vendor in subjects with PD-L1 (+) mTNBC of Cohorts A, overall population (all comers) of Cohort A and in subjects with PD-L1 strong (+) mTNBC. The point estimate 95% Agresti-Coull (A-C) confidence interval (CI) (as determined by the upper and lower 97.5% one-sided confidence bounds) will be provided based on normal approximation for the binomial distribution. Subjects without response data will be counted as non-responders.

Similarly, a supportive analysis to the primary method, ORR based on RECIST 1.1 by study site investigator and local radiology review will also be performed in the same fashion.

For the secondary endpoint of DCR, similar estimation methods used for ORR will be applied.

For DOR, PFS and OS, Kaplan-Meier (KM) curves, median estimates, and survival at 6 and 12 months based on the KM curves (95% CI is based on Greenwood's formula) will be provided as appropriate. Subjects without efficacy evaluation data or without survival data will be censored at Day 1. The restricted mean survival time (RMST) for DOR will also be provided as a supportive analysis.

Censoring rules for DOR are summarized in [Table 9](#).

Table 9 Censoring Rules for DOR

Situation	Date of progression or censoring	Outcome
No progression nor death, no new anti-cancer therapy initiated	Last adequate assessment	Censor (non-event)
No progression nor death, new anti-cancer therapy initiated	Last adequate assessment before new anti-cancer therapy initiated	Censor (non-event)
≥ 2 consecutive missed adequate disease assessments	Last adequate assessment prior to ≥ 2 missed adequate disease assessments	Censor (non-event)
Death or progression after ≤ 1 missed adequate disease assessments	Death or progression	End of response (Event)

A missed disease assessment includes any assessment that is not obtained or is considered inadequate for evaluation of response.

Similar estimation methods will be applied to the efficacy analyses for the subjects with PD-L1 (+) mTNBC in Cohort B.

[Table 10](#) summarizes the key efficacy analyses for primary and secondary endpoints in this study.

Table 10 Analysis Strategy for Primary/Secondary Efficacy Endpoints in Cohorts A and C

Endpoint/Variable (Description, Time Point)	Statistical Method	Analysis Population	Missing Data Approach
Primary:			
ORR, based on RECIST1.1 by the central imaging vendor	95% Agresti-Coull CI	ASaT - PD-L1 (+) - overall - PD-L1 strong (+)	Subjects with missing data are considered non-responders
Secondary:			
Response duration (DOR) Based on RECIST1.1 
 o by the central imaging vendor o by study site investigator and local radiology review 	Summary statistics using Kaplan-Meier method	All responders - PD-L1 (+) - overall - PD-L1 strong (+)	Non-responders are excluded in analysis
ORR Based on RECIST1.1 
 o by study site investigator and local radiology review 	Agresti-Coull 95% CI	ASaT - PD-L1 (+) - overall - PD-L1 strong (+)	Subjects with missing data are considered non-responders
DCR Based on RECIST1.1 
 o by the central imaging vendor o by study site investigator and local radiology review 	Agresti-Coull 95% CI	ASaT - PD-L1 (+) - overall - PD-L1 strong (+)	Subjects with missing data are considered non-responders
Progression-free survival (PFS) Based on RECIST1.1 
 o by the central imaging vendor o by study site investigator and local radiology review 	Summary statistics using Kaplan-Meier method	ASaT - PD-L1 (+) - overall - PD-L1 strong (+)	Censored at last assessment
Overall survival (OS)	Summary statistics using Kaplan-Meier method	ASaT - PD-L1 (+) - overall - PD-L1 strong (+)	Censored at last assessment
95% confidence interval is determined by the upper and lower 97.5% one-sided confidence bounds.			

Similar efficacy methods will be applied to Cohort B for subjects with PD-L1 (+) tumors receiving pembrolizumab as 1L monotherapy for mTNBC.

